14.5.1 Secondary Efficacy Variables and Analyses

The proportion of patients in each subtype with stable disease (SD) will be summarized after the second cycle.

The DoR will be the time from first meeting of criteria for response (ie CR or PR) to first documentation of relapse or progression.

The TTP is defined as the time from study entry (first dosing) until documented lymphoma progression or death as a result of lymphoma. Patients not experiencing a progression will be censored at the last NHL assessment. Deaths from other causes are censored at the time of death. The data will be summarized using Kaplan-Meier estimates.

Progression-free survival is defined as the time from study entry (first dosing) until lymphoma progression or death as a result of any cause. Patients not experiencing a progression or death will be censored at the last NHL assessment. The data will be summarized using Kaplan-Meier estimates.

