Duration of response (Investigator): Duration of response will be defined as the time from date of first response (CR or PR) until first date that recurrence or progressive disease is objectively documented. The duration of response will be calculated in the subgroup of all patients showing any response; confirmation of response will not be required. Patients who showed a response but did not show PD or recurrence until end of study or before study discontinuation (i.e. patients who are at least stable at their last tumor assessment) are considered censored at the timepoint of last response assessment. Deaths due to causes other than progression of disease are to be reported as SAEs and are censored for duration of

Statistical Analysis Plan Final Version 4.0

response analysis at the date of last tumor assessment before death. The cause of death has to be recorded as free text by the Investigator on the eCRF study completion page. If the cause of death does not explicitly state whether death is related to progression of disease, a query will be raised to ask the investigator to classify the relationship to disease (yes/no). Morphosys Drug Safety will assess the causality of the SAE by reviewing the corresponding SAE documents.

Time to response (Investigator): Time to response will be defined as the time from Cycle 1, Day 1 (first administration of study drug) until the date of first response (CR or PR). Patients who do not have a response to treatment will be censored at the date of their last tumor assessment.

Time to progression (Investigator): Time to progression is defined as the time from Cycle 1, Day 1 (first administration of study drug) until date of first tumor progression (which is entered in the tumor assessment module). Patients who do not show any documented progression (which is entered in the response assessment module of the eCRF) before the end of study or before study discontinuation or before death are considered censored using the last date with a tumor assessment as censoring date (irrespective of when the patient died). Deaths due to causes other than disease progression are censored.

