Duration of best overall response (Central Read): Duration of best overall response will be defined as the time from date of best overall response (as provided by the central reviewer) until first date that recurrent or progressive disease is objectively documented. The duration of

Statistical Analysis Plan Final Version 4.0

best overall response will be calculated in the subgroup of all patients showing any response; confirmation of response will not be required. Patients who showed a response but did not show PD or recurrence until end of study or before withdrawal (according to the central reviewer) are considered censored at the timepoint of last response assessment. Deaths without documented progression before death (according to the central reviewer) are also considered as censored at date of last response assessment.

Time to response (Central Read): Time to response will be defined as the time from Cycle 1, Day 1 (first administration of study drug) until the date of best overall response (as provided by the central reviewer) if best overall response is PR or CR. Patients who do not have a response to treatment will be censored at the date of their last tumor assessment.

Time to progression (Central Read): Time to progression is defined as the time from Cycle 1, Day 1 (first administration of study drug) until date of progression/relapse (as provided by the central reviewer). Patients who do not show any documented progression (according to the central reviewer) before the end of study or before withdrawal or before death are considered censored using the last date with a tumor assessment as censoring date (irrespective of when the patient died).

Progression-free survival (Central Read): Progression-free survival is defined as the time from Cycle 1, Day 1 (first administration of study drug) until date of progression/relapse (as provided by the central reviewer) or date of death from any cause (as given in the eCRF). If the patient does not show any documented progression before death (according to the central reviewer), the date of progression/death will be the date of death if death occurs within 2 months after the last date with a tumor assessment. If death occurs after 2 months after the last date with a tumor assessment or the patient did not progress or die until end of study or before withdrawal, the patient will be analyzed as censored using the last date with a tumor assessment as censoring date.

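### The SAP gives contradictory rules for duration of response when a responder dies of lymphoma without documented progression, and censoring that death would overstate the duration

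*SAP*

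**What the plan says.** **Protocol.** Section 14.5.1 defines DoR without mentioning death: "The DoR will be the time from first meeting of criteria for response (ie CR or PR) to first documentation of relapse or progression". The same section counts death from lymphoma as an event for time to progression (TTP).

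**SAP 7.3.4.1, investigator read.** Four statements in one paragraph bear on a responder's death:
- DoR runs "until first date that recurrence or progressive disease is objectively documented".
- The general censoring sentence covers "Patients who showed a response but did not show PD or recurrence until end of study or before study discontinuation", glossed as "i.e. patients who are at least stable at their last tumor assessment) are considered censored at the timepoint of last response assessment".
- The sentence on deaths reads "Deaths due to causes other than progression of disease are to be reported as SAEs and are censored for duration of", continuing "response analysis at the date of last tumor assessment before death".
- If the recorded cause of death is unclear, "a query will be raised to ask the investigator to classify the relationship to disease (yes/no"); the sponsor's drug safety group also reviews causality.

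**SAP 7.3.4.2, central read.** One rule applies regardless of cause: "Deaths without documented progression before death (according to the central reviewer) are also considered as censored at date of last response assessment".

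SAP 9.2 analyses both variables by Kaplan-Meier in responders. SAP section 12, which lists changes from the protocol, has no entry on deaths in DoR.

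**The concern.** Evaluating duration of response is the first secondary objective. For one class of patient, the responder who dies of lymphoma between assessments, the SAP does not determine the outcome. Two programmers working from SAP 7.3.4.1 could code the same patient in opposite ways and each point to a sentence in support.

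The choice affects the estimate. Kaplan-Meier assumes that a censored patient would have had the same prospects as those still at risk. A patient who has died of lymphoma would not, so censoring at the last scan credits a failed response with a chance of continuing.

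Progression can go undocumented in this study. From the end of Cycle 3, scheduled response assessments are 10 weeks to 6 months apart, because the first and third follow-up visits have none (Protocol Table 2 and 10.3). The End of Study response assessment is by physical examination only (Protocol 10.5).

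**Working it through.** The plan states no DoR median, event count or expected number of such deaths, so there is no figure to reproduce. The check has a textual part and an illustration.

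**1. One patient under each rule.** Take a responder still in remission at the last scan who then dies of lymphoma, with no progression recorded.

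| Rule | Result for this patient |
|---|---|
| 7.3.4.1, endpoint definition | No event: nothing was documented |
| 7.3.4.1, general censoring sentence | Censored at the last assessment |
| 7.3.4.1, sentence on deaths | Not among the deaths it censors, so an event by implication; no date given |
| 7.3.4.1, cause-of-death query and review | Affects DoR only if lymphoma deaths are handled differently from others |
| 7.3.4.2, central read | Censored at the last assessment |

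If the sentence on deaths governs, the investigator read counts the death and the central read does not. If the general sentence governs, both reads censor it and the cause-of-death classification changes nothing in DoR.

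**2. Direction and size, analytic.** Assumptions (not from the documents): exponential DoR, true median 12 months when lymphoma deaths count, and a share f of failures that are lymphoma deaths without documented progression. Censoring them leaves a hazard of (1 − f) × ln 2 / 12. Hence S(12) = 2^−(1−f) and the median is 12/(1−f).

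| f | 12-month DoR | Median (months) |
|---|---|---|
| 0 | 50% | 12 |
| 10% | 53.6% | 13.3 |
| 20% | 57.4% | 15.0 |
| 30% | 61.6% | 17.1 |

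For scale, 30% of 120 patients is 36 responders, if all four cohorts fill and the response rate is 30%. The standard error at 50% is then √(0.25/36) = 8.3 points. The shifts of 3.6, 7.4 and 11.6 points are 0.4, 0.9 and 1.4 standard errors.

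**3. Simulation.** This used the same true median, assessments every 3 months, 36 months of follow-up and 4,000 runs per setting. It compared censoring such deaths at the last assessment with counting them at death.
- With 9 or with 36 responders, the mean 12-month estimate rose from 0.50 to 0.53, 0.57 and 0.61 for f = 10%, 20% and 30%.
- The median was higher in 26%, 49% and 65% of runs with 9 responders, and in 53%, 80% and 93% with 36. It was lower in none.

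**4. A small example.** Let nine responses end at 2, 4, 6, 8, 10, 12, 14, 18 and 24 months.
- All counted as events: the median is 10 months, and S(12) = 3/9 = 33.3%.
- Failure at 8 months is a lymphoma death censored at a scan at 6.5 months: S(12) = 6/9 × 4/5 × 3/4 = 40.0%, and the median is 12 months.
- Failure at 2 months censored instead: the curve is 1/9 = 11.1 points higher at month 2. At month 12 it is 3/8 − 3/9 = 4.2 points higher, and at month 24 there is no difference.

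**The case against.** The strongest reply is that the protocol ends DoR at documented relapse or progression and names no death as an event, so the central rule follows the protocol and overstatement is a matter of preferred definition. In part this stands: the bias exists relative to treating lymphoma death as the end of response, which the protocol requires for TTP but not for DoR. It does not rescue SAP 7.3.4.1, which still gives two answers for one patient.

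A reader might infer that the investigator read plainly counts lymphoma deaths, so that the two DoR curves are bound to differ by rule. The documents do not support that. The event is only implied, and if the general censoring sentence governs, the reads agree on this point.

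Nor are the two variables one endpoint under two rules. The SAP names them separately and starts them differently: first response for the investigator, date of best overall response for the central read. Where best response comes later, this shortens central DoR and can mask the effect of censoring.

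A reader might also take the 11-point step with nine responders as the distortion in each subtype. It applies only just after the death, and SAP 9.2 presents DoR for all responders overall, so subtype curves may not be planned.

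Finally, the case is narrow. The patient must die on study as a responder with no recorded progression. Progression-free survival (PFS) counts deaths within 2 months of the last assessment, all deaths are tabulated and listed, no inference testing is planned, and the primary response rate is untouched. All of this limits the consequence but leaves the contradiction in place.

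**Conclusion.** The point holds as a contradiction within SAP 7.3.4.1, set beside a central rule in 7.3.4.2 that censors every death without centrally documented progression. Depending on which investigator sentence is followed, either the reads use different death rules or both censor deaths from the disease. Wherever such a death is censored, Kaplan-Meier DoR is biased upward relative to counting it as the end of response.

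The size is unknown and may be zero. The range of 13.3 to 17.1 months against a true 12 rests on an assumed exponential DoR and an assumed 10% to 30% share of such deaths; neither comes from the documents. DoR is a descriptive secondary endpoint. The correction is still worth making, because the text cannot be programmed unambiguously and the remedy is cheap.

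**What to change.** - In SAP 7.3.4.1 and 7.3.4.2, count a responder's death due to lymphoma without prior documented progression as a DoR event on the date of death. Use the cause-of-death classification in 7.3.4.1 and the eCRF death date already used for central PFS.
- Limit the general censoring sentences, and the central sentence on deaths, to patients who are alive or died of other causes.
- Show the documented-progression-only version, with lymphoma deaths censored, as a sensitivity analysis for each read.
- List the rule in SAP section 12, since the protocol's DoR definition is silent on death.
- State beside the results that the reads also start DoR at different dates, so a common death rule alone will not make the two curves fully comparable.

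The cost is SAP wording and one extra Kaplan-Meier table per read, with no new data. DoR may look slightly less favourable.

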7.3.4.2 Central Read

Additionally a central radiology read of scans will be performed by SYNARC/BioClinica. The revised IWG criteria definitions [4] will also be applied. Details of the central read are described in the Independent Review Charter, Version 1.0, 01-JUL-2013, provided by SYNARC.

The independent reviewers (two primary radiologists) will be presented with all time points sequentially in chronological order, and will provide assessments for each time point. For the

overall tumor assessment of the central read a slightly different terminology is used:

- CR - Complete response
- PR - Partial response
- SD - Stable disease
- PD - Relapsed or progressive disease
- NE - Non-Evaluable (can be applied if repeated measurements cannot be applied for reasons such as inadequate or missing imaging and when progression/relapse cannot be assigned for the visit overall response)
- ND - No Disease (this category is used if there is no tumor and there was no tumor at baseline)

Once the independent reviews for all time points in the course of the study have taken place, all time points for a particular patient will be again reviewed together by the two independent reviewers in a global patient review over all time points. In their global patient review the two independent reviewers will determine:

- best overall response (defined as best response the subject had since treatment started taking into account scheduled and unscheduled visits)
- date of the best overall response
- duration of best overall response (calculated by the system as time from first response to progression if patient is PD at a specific visit)
- date when progression/relapse occurred

Finally, an adjudicator radiologist will perform adjudication, in case there is any discrepancy in the global patient review of the two primary radiologists. The adjudicator will review both initial readings and will record a new review that will agree with either of the duplicate reviews. Thus, the adjudicator will need to agree to the complete reading of one of the primary radiologists (all assessments by visit and all variables from corresponding global review). A mandatory comment will need to be recorded. The adjudicated reading results will be considered as the results for the involved patients.

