Patients without any post-baseline response assessment will be considered as not evaluable (NE) in both the central read and investigator assessment. Patients who have been evaluated by investigator assessment, but not by central review assessment will be excluded from the concordance analysis.

The proportion (%) of patients who had at least one central review among the total number of patients who underwent at least one investigator assessment will be calculated. Moreover, the proportion (%) of the total number of central reviews among the total number of investigator assessments will be derived (i.e., the total number of central reviews across all visits and all patients divided with the total number of investigator response assessments across all visits and all patients multiplied by 100). The analysis will be conducted using the ITT population.

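### The central-read censoring dates for TTP, PFS, DoR and time to response are not limited to evaluable reads, so a final non-evaluable visit can add event-free time that no readable scan supports

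*SAP*

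**What the plan says.** SAP 7.3.4.2 introduces the visit-level categories of the central read with the words "overall tumor assessment of the central read a slightly different terminology is used". The list holds CR, PR, SD, PD, ND and one category for visits that could not be judged: "NE - Non-Evaluable (can be applied if repeated measurements cannot be applied for reasons such as inadequate or missing imaging". NE is reserved for visits at which progression or relapse cannot be assigned.

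The same section then defines the central-read time-to-event variables:

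- **TTP**, no documented progression: "before withdrawal or before death are considered censored using the last date with a tumor assessment as censoring date".
- **PFS**, no event: "the patient will be analyzed as censored using the last date with a tumor assessment as censoring date".
- **PFS**, death without documented progression: the event date "will be the date of death if death occurs within 2 months after the last date with a tumor assessment". A later death leaves the patient censored.
- **DoR**, no progression or recurrence: patients "are considered censored at the timepoint of last response assessment".
- **DoR**, deaths without documented progression: these "are also considered as censored at date of last response assessment".
- **Time to response**, non-responders: censored at the date of their last tumor assessment.

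No rule says that the assessment must be evaluable. SAP 9.2 describes the main PFS analysis with a third term, the last radiological assessment. Protocol 14.5.1 uses a fourth, the last NHL assessment. Neither is qualified.

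**The concern.** A censoring date states that the patient was known to be event-free up to that day. A visit read NE cannot support that statement, because the reader has recorded that status could not be determined. If such a visit may set the censoring date, the patient stays in the risk set for a further scan interval without having been shown to be free of progression. Too many patients are then counted as at risk at event times in that interval, each Kaplan-Meier step is too small, and the curve sits too high.

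The study is single-arm with about 30 patients per subtype that reaches Stage 2, so no comparator absorbs the error and a few dates can be visible in a curve. The error need not be random, since patients who leave in poor condition may be those with a poor or missing last scan.

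The PFS death window hangs on the same anchor. A visit with no readable scan can therefore decide whether a death counts as an event.

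**Working it through.** The plan states no figure on this point, so there is none to reproduce. The check has four parts.

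**1. Does another passage exclude NE visits?**
- SAP 7.3.4.2 also calls the radiologists' visit-level reads tumor assessments, in the paragraph on other anti-tumor treatment. The term therefore naturally covers a visit read, and NE is one value of that read.
- It says the derived variables rest only on the global patient review. The four listed outputs of that review are best overall response, its date, its duration, and the date of progression or relapse. None is a last-assessment date, so the programmer must find the censoring date elsewhere.
- Non-PD reads after other anti-tumor treatment are dropped. NE is non-PD, so this exclusion covers NE reads, but only after new therapy.
- SAP 9.1 uses NE in another sense for the concordance analysis: "Patients without any post-baseline response assessment will be considered as not evaluable (NE) in both the central read and investigator assessment". That does not bear on censoring.

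The gap is not closed.

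**2. How much time does one trailing NE visit add?** Inputs are protocol Table 2 and sections 10.2 and 10.3, and the SAP 7.1 factor of 30.4375 days per month. Cycle 2 Day 22 is study day 50. Cycle 3 starts 14 days later, so Cycle 3 Day 28 is day 50 + 14 + 27 = 91. FU1 is day 91 + 28 = 119, FU2 is 119 + 42 = 161 and FU3 is 161 + 42 = 203. FU4 to FU6 follow at 3-month steps and later visits at 6-month steps. FU3 has no response assessment.

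| From | To | Days | Months |
|---|---|---|---|
| C2D28 (day 56) | C3D28 (day 91) | 35 | 1.15 |
| C3D28 | FU2 (day 161) | 70 | 2.30 |
| FU2 | FU4 (day 294) | 133 | 4.38 |
| FU4, FU5 | FU5, FU6 | 91 | 3.0 |
| FU6 onward | next visit | 183 | 6.0 |

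If C2D28 is the only post-baseline visit and is NE, the added time is 55 / 30.4375 = 1.81 months, counted from Day 1.

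**3. What does this do to a Kaplan-Meier curve?** The documents give no NE rate, so the following are assumptions: exponential TTP with median 3, 6 or 12 months; dropout hazard 0.03 per month; each visit NE at random with probability 5%, 10% or 20%; a patient who has progressed by an NE visit leaves without a readable scan; N = 30; 1,500 runs. Entries are mean TTP survival (%), with NE visits counted / evaluable visits only.

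| Median (months) | NE rate | Month 6 | Month 12 |
|---|---|---|---|
| 3 | 5% | 32.2 / 31.2 | 12.3 / 11.2 |
| 3 | 10% | 34.3 / 32.3 | 14.8 / 12.5 |
| 3 | 20% | 39.8 / 35.5 | 19.4 / 14.3 |
| 6 | 5% | 56.0 / 55.5 | 34.4 / 33.6 |
| 6 | 10% | 58.1 / 57.1 | 37.4 / 35.7 |
| 6 | 20% | 61.8 / 59.6 | 42.0 / 38.4 |
| 12 | 5% | 75.0 / 74.7 | 59.1 / 58.6 |
| 12 | 10% | 76.2 / 75.8 | 60.8 / 59.9 |
| 12 | 20% | 78.6 / 77.7 | 64.1 / 62.4 |

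The difference runs from 75.0 - 74.7 = 0.3 to 19.4 - 14.3 = 5.1 points. A repeat run under the same assumptions gave the same median under both rules in 80% to 97% of runs. If progressed patients instead stay on study and are read at the next visit, the difference falls to 0.1 to 0.9 points. The larger figures therefore depend on patients leaving after an unreadable progression.

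**4. PFS death window.** Take a last readable scan at FU4 ((294 - 1) / 30.4375 = 9.6 months), FU5 read NE (12.6 months) and death at 13.6 months. Anchored on FU5, the death falls 13.6 - 12.6 = 1.0 month later and is an event at 13.6. Anchored on FU4, the interval is 13.6 - 9.6 = 4.0 months and the patient is censored at 9.6.

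**The case against.** The best defence is that the SAP nowhere says NE visits count. The category list only invites that inference. A missing scan may supply no assessment date at all, and details of the central read are referred to an Independent Review Charter that is not among the documents. This stands as far as it goes: the text fails to exclude NE, which is less than expressly including it. But 7.3.4.2 defines these endpoints itself and does not defer to the Charter for the censoring date.

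Some stronger readings are tempting and should be resisted.

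- *Medians are inflated in proportion to the added follow-up.* Progression is mostly dated at scan visits, so Kaplan-Meier medians tend to fall on scan dates and often stay put.
- *Central PFS is lengthened.* An NE visit adds censored time for some patients, but it can also turn a censored death into an event.
- *The central and investigator reads are censored on different footings.* Investigator TTP and PFS use the same anchor. The investigator list has no NE category, though it has one for assessments not done.
- *No event can be seen at an NE visit.* NE applies only when progression cannot be assigned, so progression visible on incomplete imaging can still be read as PD.

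Two features limit the exposure. Non-PD reads after new therapy are dropped. SAP 9.2 also has a PFS sensitivity analysis that counts withdrawal for disease progression as an event without radiological confirmation; it does not extend to TTP or DoR.

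**Conclusion.** The point holds as a defect in the central-read censoring rule. Followed literally, it lets a visit the reader could not assess set the censoring date for central TTP, PFS, DoR and time to response. One trailing NE visit adds about 1.15 to 6 months of unsupported event-free time. The bias is upward for the TTP and DoR curves and of mixed direction for PFS.

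The size is conditional. At assumed NE rates of 5% to 20% of visits, TTP estimates at 6 and 12 months come out about 0.3 to 5 percentage points higher than with evaluable-only censoring. The upper part of that range needs a high NE rate and patients who leave after an unreadable progression. DoR and PFS were not simulated.

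A reader might infer that the trial's main result is at risk. It is not: the primary endpoint is investigator-assessed ORR (SAP 2.2.1), and protocol 14.10 plans no inferential testing. The affected results are the central-read versions of the secondary time-to-event analyses. Severity is minor.

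**What to change.** In SAP 7.3.4.2, define one date: the last central visit read with an evaluable result (CR, PR, SD or ND; not NE). Use it to censor central TTP, PFS in patients without an event, DoR, and time to response. If there is no evaluable post-baseline read, censor TTP, PFS and time to response at Day 1. Name the by-visit read as the source, since the global review supplies no such date. Say also how to treat a visit that one radiologist could read and the other called NE without adjudication; the existing worst-of-two rule does not rank NE.

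Treat the 2-month PFS death window separately. Moving its anchor to the last evaluable read can remove death events, so it is a trade-off and should not be presented as bias removal. State which anchor the main analysis uses, show the other as a sensitivity analysis, and bring the SAP 9.2 wording into line.

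The cost is one definition, one filter in the derivation program and one extra PFS run, with no new data. Central follow-up becomes slightly shorter and the estimates slightly less favourable. The change corrects only the censoring date: in the 6-month, 10% NE scenario the month-6 estimate falls from 58.1% to 57.1% against an assumed true 50.0%. Most of the remaining excess comes from progression being seen only at visits and from progressed patients leaving unread.
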